6.8.1.1 Concomitant Procedures

A concomitant procedure is any therapeutic intervention (eg, surgery/biopsy, physical therapy) or diagnostic assessment (eg, blood gas measurement, bacterial cultures) performed between signing of the informed consent and the participant's last protocol-specified study visit.

All concomitant procedures must be recorded in the eCRF until 28 days after each study vaccine. Thereafter, only concomitant procedures associated with an SAE, MAAE, or evaluation of COVID-19 cases will be entered in the eCRF.

6.9 Dose Modification

No dose modifications will be allowed.

6.10 Intervention After the End of the Study

No intervention will be provided to study participants after the EOS.

7 STUDY ASSESSMENTS

Technical considerations for study assessments are described throughout Section 4 of the protocol.

The schedule of study assessments is provided in [Appendix 1](#).

7.1 Efficacy Assessments

7.1.1 Evaluation of Participants With Suspected COVID-19

Participants with suspected COVID-19 will be evaluated for the presence of potential symptoms and clinical findings of COVID-19 as tabulated in [Appendix 2](#).

To be considered as a protocol-defined COVID-19 case, virological confirmation (by RT-PCR) of SARS-CoV-2 and demonstration of at least one of the symptoms or clinical findings listed in [Appendix 2](#) are required. This criterion may be met by any of the following tests:

RT-PCR test or other equivalent nucleic acid amplification-based test (NAAT). Results from lab test will only be considered acceptable if it was obtained using:

- An assay accredited by the Vietnamese MOH;
- Additional accreditation of the assay by FDA is also preferred;
- OR an assay performed in a laboratory that is currently CLIA-certified;
- OR an assay performed by a laboratory accredited according to the ISO 15189 standard.

Note: For Phase 1/2/3a/3b, nasal swabs for RT-PCR test do not need to be performed after Day 92. For Phase 3c, nasal swabs should continue to be collected until the last study visit (early termination of Day 394).

Case definitions for the evaluation of COVID-19 and severe COVID-19 are provided in [Appendix 2](#). All suspected COVID-19 cases will undergo tiered review:

- All SARS-CoV-2-confirmed cases are reviewed by a blinded, independent adjudication committee (AC) against the symptoms and scales provided in [Appendix 2](#). The AC will determine if the severity of symptoms of COVID-19 accompanying SARS-CoV-2 virological confirmation aligns with protocol-defined COVID-19 case definitions, asymptomatic SARS-CoV-2 infection, or atypical COVID-19 case presentations. COVID-19 cases (protocol-confirmed and atypical) will also be evaluated by severity using FDA and World Health Organization (WHO) criteria.

7.1.1.1 Severe COVID-19

Two definitions will be used to define severe COVID-19: FDA and WHO ([Appendix 2](#)). Confirmed COVID-19 must meet the protocol-defined COVID-19 case definition and either the FDA or the WHO criteria for severe COVID-19 in order to be considered an event of Severe COVID-19 for evaluation of this endpoint. These criteria are summarized in [Appendix 2](#).

7.1.1.2 Asymptomatic COVID-19

Asymptomatic SARS-CoV-2 infection is defined as a participant with a positive NAAT test for SARS-CoV-2 without the presence of protocol-specified COVID-19 ([Appendix 2](#)) or atypical COVID-19 symptoms. These cases will be collected as disease events but not analyzed towards COVID-19 cases.

7.1.1.3 Atypical COVID-19

Atypical COVID-19 is defined as a participant with a positive NAAT test for SARS-CoV-2 virus and contemporaneous symptoms that are not those listed in [Appendix 2](#) but nevertheless clinically suspected to represent a manifestation of COVID-19. These cases will be used for exploratory analyses of COVID-19 cases only.

7.1.1.4 Death Attributed to COVID-19

Any participant who dies during study participation will be evaluated for suspected/confirmed causes of death. Autopsy results and histopathology results, as available, will be requested. Any death attributed to confirmed COVID-19 will be evaluated for the death endpoint. For cases of clinical suspicion of COVID-19 as the cause of the death, these cases will be subject to review by the blinded AC for confirmation of whether these meet the 'Death Attributed to COVID-19' endpoint.

7.2 Immunogenicity Assessments

For Phase 1, Phase 2, Phase 3a and Phase 3c-1 participants, blood samples for immunogenicity assessments will be collected at the time points indicated in Section [4.5.5.3](#) and the Schedule of Assessments ([Appendix 1](#)). On Days 1, 29, and 92, blood samples for immunogenicity assessment will be collected before administration of each study vaccine. The following analytes will be measured:

- 1) Assays run at National Institute of Hygiene and Epidemiology, Department of Virology, Vietnam
 - a) Serum NAb titer against SARS-CoV-2:
 - i. Genscript SARS-CoV-2 surrogate virus neutralization test (sVNT): This sVNT assay is a functional Enzyme-Linked Immunosorbent Assay (ELISA) intended for qualitative or semi-quantitative detection of total neutralizing antibodies in human serum, K2-EDTA plasma, peripheral blood and blood plasma that block the binding of SARS-CoV-2 to the human ACE2 receptor of host cells. This binding assay has been shown to correlate well with cell-based neutralizing antibody assays. When run with an appropriate reference standard, the data can be converted to international units using the WHO reference standard conversion. The assay will be performed on samples from participants in Phase 1/2/3a. It may also be performed on samples from participants in Phase 3c-1.
 - ii. Plaque reduction neutralization test [PRNT]: This live virus assay is performed in a biosafety level 3 (BSL3) laboratory using a Wuhan reference standard

strain and delta variant strain isolated at the Department of Virology, National Institute of Hygiene and Epidemiology. Neutralizing antibody titers are calculated as the highest serum dilution that results in 50% reduction in the number of virus plaques (PRNT50). This assay will be performed on samples from all participants in Phase 1 and the first 50 participants in Phase 2. It may also be performed on samples from additional participants in Phase 2/3a and/or 3c-1.

- iii. Genscript SARS-CoV-2 pseudovirus neutralization (MNT) assay kit Luc reporter: this kit provides a cell-based functional assay for measuring the potency of candidate drugs in neutralizing SARS-CoV-2 S protein. The S protein described in this kit is located on the surface of the lentivirus-based pseudovirus particles, so the pseudovirus can bind to the ACE2 receptor overexpressed on the target cells, simulating the fusion process of the coronavirus-cell and cell-cell membrane. After infection, the pseudovirus can express the luciferase gene in the target cell. By measuring the bioluminescence signal, the extent of pseudovirus infection can be determined. When a candidate drug that is able to neutralize SARS-CoV-2 binds to the S protein, the interaction of ACE2 and S proteins on the pseudovirus is blocked, preventing the pseudovirus infection and resulting in a decrease in the bioluminescence signal. Therefore, the sample potential for neutralizing SARS-CoV-2 can be determined from the signal reduction. This assay may be performed on samples from participants in Phase 3c-1 and on samples from participants in Phase 1/2/3a.
- b) Serum IgG antibodies binding the SARS-CoV-2 spike protein
 - i. Siemens ADVIA Centaur XP/XPT system: this is a fully automated 2-step antigen sandwich immunoassay using acridinium ester chemiluminescent technology. The solid phase contains a preformed complex of streptavidin-coated microparticles and biotinylated SARS-CoV-2 recombinant antigens. This reagent complex is used to capture full-length SARS-CoV-2 S protein-specific antibodies in the patient samples. This assay will be performed on samples from participants in Phase 1/2/3a and 3c-1.

2) Assays run at PPD BioA Labs in Richmond, VA, USA

- a) Serum NAb titer against SARS-CoV-2
 - i. Pseudovirus microneutralization test (MNT; (Wuhan-Hu-1 [D614G strain])): The SARS CoV-2 MNT is a cell-based assay that is designed to determine the ability of anti-SARS CoV-2 Spike neutralizing antibodies to inhibit the infection of 293T-ACE2 cells by D614G strain-specific SARS CoV-2 Spike Reporter Virus Particles (RVP) which express green fluorescent protein (GFP). Results can be converted to IU/mL using a WHO reference standard calibration factor. This assay will be performed on samples from all participants in Phase 1 and the first 150 participants who received ARCT-154 in the initial vaccination

series in Phase 2. This assay may also be performed on samples from additional participants in Phase 1/2/3a and/or participants in Phase 3c-1.

- ii. ACE2 receptor binding inhibition sVNT assay: The V-PLEX COVID-19 Coronavirus (ACE2) Kit is a multiplex neutralization assay that measures the antibodies capable of blocking the binding of angiotensin-converting enzyme 2 (ACE2) to the SARS-CoV-2 Spike and RBD antigens. The Panel serves as a high-throughput alternative to traditional neutralization assays. The Panel 13 (IgG) Kit is a multiplex serology assay for antibodies to ten Spike antigens from variants of SARS-CoV-2, including the Alpha, Beta, Gamma, Delta, and several emerging variants. Panel 13 has Spike antigens from the following lineages: A (WT), (B.1.1.7), (B.1.351), (B.1.526.1), (B.1.617), (B.1.617.1), (B.1.617.2), (B.1.617.3), (P.1), and (P.2). This assay will be performed on samples from all participants in Phase 1 and the first 150 participants who received ARCT-154 in the initial vaccination series in Phase 2. This assay may also be performed on samples from additional participants in Phase 1/2/3a and/or participants in Phase 3c-1.
- iii. Delta virus MNT: This is a cell-based assay designed to determine the ability of anti-SARS CoV-2 Spike neutralizing antibodies to inhibit the infection of 293T-ACE2 cells by Delta strain-specific SARS CoV-2 Spike Reporter Virus Particles (RVP) which express green fluorescent protein (GFP). The readout is ID50. This assay will be performed on samples from all participants in Phase 1 and the first 150 participants who received ARCT-154 in the initial vaccination series in Phase 2. This assay may also be performed on samples from additional participants in Phase 1/2/3a and/or participants in Phase 3c-1.

b) Serum IgG antibodies binding the SARS-CoV-2 spike

- i. Mesoscale Discovery (MSD) multiplex assay. MSD multiplex indirect binding ECL is a quantitative electrochemiluminescence (ECL) assay designed to detect antibodies to total immunoglobulin G (IgG) against the full-length spike, RBD, and N antigens of the Wuhan strain SARS-CoV-2. Results can be converted to BAU/mL using WHO reference standard calibration factors provided by MSD. This assay may be performed on samples from participants in Phase 1/2/3a and/or Phase 3c-1.

Additional testing may also be performed using other assays.

Immunogenicity laboratory results will only be considered acceptable if obtained using an assay accepted by the Vietnamese MOH.

Sample aliquots will be designed to ensure that backup samples are available and that adequate vial volumes may allow for further testing. The actual time and date of each sample collected will be recorded in the eCRF, and unique sample identification will be used to maintain the blind at the laboratory at all times and to allow for automated sample tracking and storage. Handling and preparation of the samples for analysis, as well as shipping and storage requirements, will be provided in a separate study manual.

7.3 Reactogenicity

Reactogenicity will be evaluated in all participants enrolled in the study (Section 7.4.1.1.1). Reactogenicity will be evaluated following receipt of each vaccination of the initial series and evaluated in those participants who provide at least 1 response to the Diary. Further details on the reactogenicity analysis set are provided in Section 8.2.

Participants will complete a Diary collecting solicited AEs for 7 days following each vaccine administration of the initial series.

7.4 Safety Assessments

Safety assessments will include monitoring and recording of solicited and unsolicited AEs, MAAEs, AEs leading to discontinuation of the study vaccine/study withdrawal, SAEs, vital signs, body temperature and (in participants who are evaluated for suspected COVID-19) pulse oximetry.

For Phase 1 participants, safety blood sampling will include CBC, chemistry panel. Virology testing (HbsAg, HCV Ab, and HIV) will also be performed at Screening. Procedures for collection, handling, and storage of blood collected for safety assessments will be detailed in the Laboratory Manual.

7.4.1 Adverse Events

In this study, AEs include subcategories of AEs collected by solicitation of participants as to types of signs and symptoms observed following vaccination (reactogenicity), referred to as “solicited AEs”, and a general category of unsolicited AEs that includes any spontaneously reported or observed AE occurring after the signing of informed consent.

7.4.1.1 Definitions

7.4.1.1.1 Adverse Events

The investigator is responsible for reporting all AEs that are observed or reported during the study, regardless of their relationship to the study vaccine or their clinical significance. AE collection will begin after the signing of informed consent; however, AEs that occur prior to the administration of first dose of study vaccine (ie, non-treatment-emergent AEs) will be listed separately in the clinical study report.

An AE is defined as an untoward medical occurrence associated with the use of a medicinal product in humans, whether or not considered related to the medicinal product.

An AE can therefore be any of the following:

- Any unfavorable and unintended sign (including an abnormal laboratory finding), symptom, or disease temporally associated with the use of the study vaccine, whether or not considered related to the study vaccine
- Any new disease or exacerbation of an existing disease (a worsening in the character, frequency, or severity of a known condition)

- Recurrence of an intermittent medical condition (eg, headache) not present at baseline
- Any deterioration in a laboratory value or other clinical test (eg, electrocardiogram, X-ray) that is associated with symptoms or leads to discontinuation from the study vaccine

7.4.1.1.1.1 Solicited adverse events

The term “reactogenicity” refers to selected signs and symptoms (“reactions”) occurring in the hours and days following a vaccination. These signs and symptoms are collected as solicited AEs from participants by use of the Diary for 7 consecutive days following each of the first 2 study vaccine administrations.

- The following solicited AEs are included in the Diary:
 - **Solicited local AEs:** injection site erythema, injection site pain, injection site induration/swelling, and injection site tenderness
 - **Solicited systemic AEs:** arthralgia, chills, diarrhea, dizziness, fatigue, fever (categorized by measured body temperature), headache, myalgia, and nausea/vomiting

The occurrence of each of these solicited AEs is regarded as a vaccine-related AE.

Also solicited from participants but not categorized as an AE is the use of antipyretics and analgesics to prevent or treat solicited AEs.

Solicited AEs are graded for severity according to scales defined in the Center for Biologics Evaluation and Research’s Guidance: Toxicity Grading Scale for Healthy Adult and Adolescent Volunteers Enrolled in Preventive Vaccine Clinical Trials ([DHHS 2007](#)), [Appendix 4](#).

Solicited AEs may also lead to circumstances that warrant collection of the events as unsolicited AEs. This includes any solicited AE that leads to:

- a medically attended visit
- an SAE
- a discontinuation of study vaccine
- a withdrawal from the study
- or any solicited AE that persists beyond 7 days after the first study vaccine administration.

Furthermore, should the site determine that the participant experienced and failed to enter a Grade 3 or Grade 4 solicited AE in the Diary during the time when the Diary was accepting data entry, this Grade 3 or Grade 4 solicited AE should be entered as an unsolicited AE in the CRFs.

7.4.1.1.1.2 Unsolicited adverse events

Unsolicited AEs are defined as any spontaneously reported or discovered AE.

Unsolicited AEs will be collected in all participants who receive at least 1 dose of study vaccine and are classified according to the following:

- mild, moderate, or severe
- whether or not the AE was categorized as an SAE, an MAAE, and/or an AE leading to discontinuation/withdrawal
- whether or not the AE was related to study vaccine or study procedure in the judgment of the investigator

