3.2 Phase 3b

3.2.1 Phase 3b Primary Objectives and Endpoints

The primary objectives and endpoints for Phase 3b are presented in [Table 5](#). These form the primary objectives and endpoints for the study overall.

Table 5 Phase 3b Primary Objectives and Endpoints

Phase 3b Primary Objectives	Endpoint Description
1. To assess the safety and reactogenicity of ARCT-154 compared to placebo	
Safety will be evaluated in all participants in the Phase 3b SAS and will be summarized for each vaccination as number and percentage of participants with:
 
• Any unsolicited AE starting within 28 days after each study vaccine administration, summarized by severity and relationship to study vaccine.• Any medically attended adverse event (MAAE), serious adverse event (SAE), or AE leading to discontinuation/withdrawal through Final Visit/Early Termination (ET) summarized by relationship to study vaccine. 
Reactogenicity will be evaluated in the Phase 3b RAS and will be summarized following vaccinations on Day 1 and Day 29 only as the number and percentage of participants with:
 
• Any solicited local or systemic AE starting within 7 days after each study vaccine administration by toxicity grade.
2. To evaluate the efficacy of ARCT-154 and placebo for the prevention of virologically confirmed COVID-19	
Efficacy will be evaluated in all participants in the Phase 3b mITT. The endpoint to be evaluated is as follows:
 
• The first occurrence of confirmed, protocol-defined (Appendix 2) COVID-19 with onset between Day 36 and Day 92 inclusive.

Abbreviations: AE=adverse event; COVID-19=coronavirus disease 2019; MAAE=medically attended adverse event; SAE=serious adverse event; ET=early termination

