7.4.1.2.1 Assessment of Severity

The severity, or intensity, of an AE refers to the extent to which an AE affects the participant's daily activities. Changes in the severity of an AE should be documented to allow an assessment of the duration of the event at each level of intensity. AEs characterized as intermittent do not require documentation of onset and duration of each episode.

Unsolicited AEs: The intensity of unsolicited AEs will be rated as mild, moderate, or severe using the following criteria:

Mild:	These events require minimal or no treatment and do not interfere with the participant's daily activities. OR An event usually transient in nature and generally not interfering with normal activities.
Moderate:	These events result in a low level of inconvenience or concern with the therapeutic measures. Moderate events may cause some interference with normal functioning. OR An AE that is sufficiently discomforting to interfere with normal activities.
Severe:	These events interrupt a participant's usual daily activity and may require systemic drug therapy or other treatment. Severe events are usually incapacitating. OR An AE that is incapacitating and prevents normal activities.

Solicited AEs: The intensity of solicited AEs will be graded for severity as Grade 0, Grade 1 (mild), Grade 2 (moderate), Grade 3 (severe), or Grade 4 (potentially life threatening). Further details on the toxicity grading scales are provided in [Appendix 4](#).

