7.4.1.2.2 Assessment of Causality

The investigator's assessment of an unsolicited AE's relationship to the study vaccine is part of the documentation process, but it is not a factor in determining what is or is not reported in the study. If there is any doubt as to whether a clinical observation is an AE, the event should be reported.

The relationship or association of the study vaccine in causing or contributing to the AE will be characterized using the following classification and criteria:

Related: There is a ‘reasonable possibility’ that the reported adverse event was caused by the study vaccine. ‘Reasonable possibility’ means that there is evidence to suggest a causal relationship between the event and the study vaccine.

Unrelated: There is not a ‘reasonable possibility’ that the adverse event was caused by the study vaccine.

Solicited AEs are, by definition, regarded as related to study vaccine. Therefore, causality is not assessed.

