### 6.6.1.1 Solicited Adverse Events (Reactogenicity)

The term “reactogenicity” refers to selected signs and symptoms (“reactions”) occurring in the hours and days following a vaccination. These signs and symptoms are collected as solicited AEs from participants during the 30 minute observation period after vaccination and by use of the Diary for 7 consecutive days following each study vaccine administrations. The following solicited AEs are included in the Diary:

- **Solicited local AEs:** injection site erythema, injection site pain, injection site induration/swelling, and injection site tenderness
- **Solicited systemic AEs:** arthralgia, chills, diarrhea, dizziness, fatigue, fever (categorized by measured body temperature), headache, myalgia, and nausea, vomiting

Solicited AEs are captured in the following way:

- Participant’s data recorded directly on the Diary (paper or eDiary, primary analysis)
- Investigator’s re-assessed data

Analysis of reactogenicity data will be performed based on the participant’s data recorded on the Diary/eDiary.

Reactogenicity will be analyzed after each vaccine dose (within 30 minutes or during first 7 days after the dose - refer to Table 8 for timepoints available). Participants will be considered for the computation of percentages in the specified time interval if they received the study vaccine and provided at least 1 reactogenicity diary report in the specified interval. Participants whose data are completely missing within the summary of event and timepoint (i.e no answer to a reaction category for the specific timepoint) will not be included in both numerator and denominator. For each time interval and reaction category the number of participants without missing data will be presented.

Severity of solicited local and systemic reactions will be graded as follows: grade 0 (none), grade 1 (mild), grade 2 (moderate), grade 3 (severe), and grade 4 (potentially life threatening). For participants with more than one episode of the same event in a reporting period, the event of greatest severity will be used in any summary.

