	antinucleocapsid antibody or neutralizing antibody (as assessed by sVNT for Phase 1/2/3a and MNT for Phase 3c) indicating exposure to SARS-CoV-2 prior to vaccination or SARS-CoV-2 infection prior to 7 days (inclusive) after the second study vaccination dose (Day 35).	other COVID-19 positive test or seropositivity for anti-nucleocapsid antibody indicating exposure to SARS-CoV-2 prior to vaccination or SARS-CoV-2 infection prior to 7 days (inclusive) after the second study vaccination dose (Day 35).  Note: This also impacts mITT and IAS analysis sets definitions where IcEv3 is considered.	assessment of early infection
Section 8.3.1 Table 15 (estimand 1 – Rationale for Strategies)	IcEv4 and IcEv5 could also be potentially confounding but it is more difficult to determine the precise timing of these events, so a principal stratum strategy is used to exclude these participants from immunogenicity analyses.	IcEv4 and IcEv3 could also be potentially confounding but it is more difficult to determine the precise timing of these events, so a principal stratum strategy is used to exclude these participants from immunogenicity analyses.	Correction
Section 8.3.1 Table 17 (estimand 3 – unsolicited Aes - Intercurrent Event (IcEv) Strategy)	Intercurrent Event (IcEv) Strategy:  IcEv2 (Non-study vaccine): treatment policy strategy  IcEv5 (Confounding On-study Medications): composite strategy	IcEv2 (Non-study vaccine): while on treatment strategy  IcEv5 (Confounding On-study Medications): treatment policy strategy	IcEv2: Correction of the name of the strategy to reflect the fact that events occurring after IcEv2 will not be included in the analysis as specified in protocol  IcEv5: Correction of the name of the strategy to reflect the fact that events occurring after IcEv5 are included in the analysis as specified in the protocol
Section 8.3.1 Table 17 (estimand 4 – Reactogenicity - Rationale for Strategies)	Events occurring after IcEv2, IcEv3 and IcEv5 could contribute spurious reactogenicity data so a treatment policy is used for these events and events occurring after	All solicited events will be analyzed regardless of occurrence of intercurrent events.	Reactogenicity is participant reported outcome, which will be analyzed as it is without modification.

	these IcEv's will be summarized separately		

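### Grade 3-4 solicited reactions missing from the diary have no route into the 7-day by-grade reactogenicity tables, so on this account those tables can only understate severe reactions

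*Protocol*

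**What the plan says.** The Phase 3b primary safety objective includes "Any solicited local or systemic AE starting within 7 days after each study vaccine administration by toxicity grade" (protocol section 3.2.1), and protocol section 8.4.2 makes the Phase 3b reactogenicity results part of the overall primary safety endpoints.

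Protocol section 7.4.1.1.1.1 provides for the case where a participant had a Grade 3 or 4 solicited reaction but did not record it while the diary was open: "this Grade 3 or Grade 4 solicited AE should be entered as an unsolicited AE in the CRFs".

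SAP section 6.6.1.1 names two captured sources for solicited reactions, the participant's diary (marked as the primary analysis) and the investigator's re-assessed data. It then states: "Analysis of reactogenicity data will be performed based on the participant’s data recorded on the Diary/eDiary". A reaction within 7 days counts as present if the participant answered yes in the diary. A participant with no answer for a reaction and timepoint leaves both numerator and denominator. A participant with no diary report is outside the reactogenicity analysis set (SAP section 4.1).

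For unsolicited events, protocol section 7.4.1.2.1 sets a different scale: "The intensity of unsolicited AEs will be rated as mild, moderate, or severe using the following criteria". Protocol section 7.4.1.2.2 says of solicited events: "Solicited AEs are, by definition, regarded as related to study vaccine". Unsolicited events instead receive an investigator causality judgement.

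**The concern.** The protocol foresees missed severe entries and wants them kept. The SAP does not carry that through to the table where a reader looks for severe reactogenicity. Investigator re-assessed data are captured, but no analysis of them is described. SAP section 6.6.1.2 lists the kinds of solicited event that can become unsolicited and omits this one, so no count of these events is planned either. A reader of the by-grade tables could not tell whether the number left out is zero or large enough to matter.

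At stake is the Grade 3-4 rate after each dose, the most important part of the reactogenicity profile. For primary efficacy, SAP section 6.4 adds a sensitivity analysis using CRF cases beyond the main, adjudicated source. Primary reactogenicity has no matching check.

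**Working it through.** The plan states no figure on this point, so there is nothing to reproduce. The check follows one missed Grade 3-4 reaction through the documents.

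**Step 1: which 7-day row it reaches.** The result depends on the diary.
- Diary says no: the participant is counted as having no such reaction.
- Diary shows a lower grade: the participant is counted in the lower-grade row.
- Item wholly blank: the participant leaves numerator and denominator for that reaction and timepoint.
- No diary report: the participant is outside the analysis set.

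In none of the four is the event counted as Grade 3-4. No rule works in the other direction, so the effect of this gap is one-sided.

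**Step 2: what survives on the unsolicited page.**
- Severity has three levels, judged by the effect on daily activities. Several Grade 3 criteria in protocol Appendix 4 are measurements: erythema or induration above 10 cm, fever of 39.0-40 °C. An erythema above 10 cm that does not disturb activity is Grade 3 on the solicited scale but could be rated mild here.
- Relatedness becomes a judgement instead of a definition.
- The event is tabulated with all other unsolicited AEs by system organ class, preferred term and severity (SAP section 6.6.1.2), with nothing to show that it is a missed solicited reaction.

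**Step 3: size, by assumption only.** Let p be the true Grade 3-4 rate and f the share of those reactions known to the site but missing from the diary.
- Diary says no or shows a lower grade: rate shown = p(1 − f).
- Item blank: rate shown = p(1 − f)/(1 − pf).

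Both are below p. With about 8,000 ARCT-154 recipients in Phase 3b (protocol section 8.5.2), the number absent from the Grade 3-4 rows is at most 8,000 × p × f:
- p = 1%, f = 1%: 8,000 × 0.01 × 0.01 = 0.8, about 1 participant.
- p = 10%, f = 10%: 8,000 × 0.10 × 0.10 = 80 participants.
- p = 3%: 8,000 × 0.03 = 240 true cases. With f = 5% to 20%, 12 to 48 are missed, and the table shows 228/8,000 = 2.85% to 192/8,000 = 2.40%. If the items are blank instead, f = 20% gives 0.024/0.994 = 2.41%.

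Neither p nor f is in the documents. The counts are upper limits for the any-reaction rows: SAP section 6.6.1.1 takes the greatest severity per participant in the period, so someone who missed one entry may still count through another.

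**The case against.** The strongest reply has five parts.

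1. **The rule adds capture.** A reader might infer that it removes severe events from the record. It does not: an event never entered is already absent from the diary, and the rule saves it elsewhere. Missed Grade 1-2 entries get no such rescue. This stands. The gap lies in the SAP, which does not use what the rule collects.

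2. **The events stay within primary safety reporting.** Unsolicited AEs by severity and relationship belong to the same primary objective. Grade 4 in Appendix 4 is for most terms an emergency room visit or hospitalization, so most Grade 4 events would also appear as medically attended or serious AEs (SAP section 6.6.1.3). This also stands, and it means the loss falls mainly on Grade 3 reactions that were not medically attended.

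3. **Some CRF-recorded reactions are graded.** The 30-minute observation period uses CRF data and has its own by-grade tables. A reader might infer that a severe reaction missing from the diary reaches no by-grade table at all. That is too broad: the point concerns the 7-day tables.

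4. **Diary-only analysis is a deliberate choice.** SAP section 7.1 says: "Reactogenicity is participant reported outcome, which will be analyzed as it is without modification". Keeping the diary primary is defensible. But that sentence is the reason given for a change in intercurrent-event handling. It does not discuss missed severe entries or explain why no supplementary analysis is planned.

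5. **Non-entry may be rare, and no decision hangs on it.** The protocol provides diary training, eDiary prompts and contacts at least 7 days after each dose, and safety has no hypothesis test. The effect may be small. Without a count, nobody can show that it is.

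**Conclusion.** The data flow is clear from the text: missed Grade 3-4 solicited reactions go to the unsolicited page, and the 7-day by-grade tables are built from the diary with no return path. On this account those tables can only understate Grade 3-4 reactions. The amount cannot be estimated from the documents. The 1-80 participants above, and the fall from 3% to 2.40-2.85%, are illustrations that rest wholly on assumed rates.

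A reader might also infer that the understatement falls mainly on ARCT-154 and narrows the contrast with placebo. That is plausible if severe reactions are concentrated in that arm, but the documents give no rates of severe reaction or non-entry by arm, so it remains inference.

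This is a worthwhile, inexpensive improvement to a primary safety summary. It does not invalidate the safety analysis.

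**What to change.** Keep the diary table as primary. In SAP section 6.6.1.1 add two outputs.

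(a) **A count by arm and dose** of solicited-term events with onset within 7 days that are recorded in the CRF or the investigator's re-assessed data as Grade 3-4 or severe but are absent from the diary or lower there. De-duplicate against the diary, and leave out events that reached the AE page only for medical attendance, seriousness or persistence beyond 7 days.

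(b) **One sensitivity by-grade table per reactogenicity analysis set** that merges these events with the diary data and treats them as related. Take the grade from the re-assessed data where available. Otherwise show the event as Grade 3 or 4, not distinguished, because the unsolicited page holds no toxicity grade.

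Use one denominator rule for everyone, either the reactogenicity analysis set or all vaccinated participants. Bringing in people without a diary only when they had a severe event would select on outcome and bias the rate upward.

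The cost is one count and one table per analysis set, plus a mapping by term and onset day. No new data are needed, and SAP section 2.1 places the final analysis after SAP approval. A change to the protocol wording would not help data already collected. The small downside is that the added events are ascertained by the site, not reported in the diary, so the two versions should stand side by side.
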